The cervical mobilization and stretching exercise techniques were performed by a licensed physical therapist who has 6 years of experience in manual physical therapy.

Self-administered stretching exercises were performed by participants in the combined intervention group to the following muscles: the extensor muscles, the upper part of the trapezius, and the posterior scalene ⁶. Each movement was held for 30 seconds and repeated 3 times. Lastly, the participant was instructed to perform a neck straightening exercise by retracting the neck (Chin tuck) 5 times for 3-5 seconds. Subjects in the combined intervention group were provided with written instruction of the stretching exercises and directed to perform stretching exercise 5 times a week, each exercise session takes about 10 minutes. Patients were also instructed to keep a stretching diary to track their stretch exercise frequency.

Data collection:

Data was collected at baseline, one week after intervention, and week 4. The final data collection date was set at week 8 as a follow up to determine whether the participant was able to maintain gains at one month following the interventions.

Statistical Analyses

A sample size of 50 participants was estimated using a moderate effect size of 0.25, level of significance 0.05, and power of 0.80. Data was summarized using mean and standard deviation ¹ for quantitative variables and counts (%) for qualitative variables. The normality of continuous variables was examined using Shapiro Wilk's test. The distribution of the participants' characteristics by study group were evaluated using chi-square for qualitative variables and independent t- test for quantitative variables. Mixed factorial analysis of variance (ANOVA) was used to examine changes in cervical ROM variables, pressure pain threshold, NPRS, GROC, and NDI scores by study group over time. Post hoc comparisons using Bonferroni test and effect size were computed to identify significant differences over time. We compared percent change (4 weeks vs. baseline) for all outcome variables between the two study groups using independent t- test and Mann- Whitney test. To examine whether there were any changes in the outcome variables at 4 weeks follow up paired t- test was used. The level of significance was set at $p \leq 0.05$. Statistical analysis was performed using IBM SPSS Software version 24 for Windows (Chicago, IL, USA).

Results

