There was a significant difference in mean ROM during left lateral flexion over time ($F_{2,72}=3.0$, $p=0.03$, $\eta^2=0.30$), and a significant group by time interaction ($F_{2,72}=3.0$, $p=0.03$). Bonferroni post hoc comparison revealed that the difference was significant between baseline and one week later (43.0 ± 1.1 vs. 46.3 ± 1.0 , $p=0.01$), baseline and 4 weeks later (43.0 ± 1.1 vs. 48.5 ± 1.3 , $p<0.001$), and between one week later and 4 weeks (46.3 ± 1.0 vs. 48.5 ± 1.3 , $p=0.01$). In addition, the percent improvement from baseline to 4 weeks later was significantly more for the combined intervention as compared to the standard intervention group (20.0% vs. 7.7% ; $t=2.1$, $p=0.02$).

For the other ROM directions, flexion, right rotation, and left rotation, both groups had a significant improvement in mean ROM over time ($p<0.05$), however, this improvement was not significantly different between the two groups. (Refer to **Table 2**).

Change in Pressure Pain Threshold (PPT)

There was a significant difference in mean right upper trapezius muscle pressure pain threshold over time ($F_{2,72}=4.3$, $p=0.02$, $\eta^2=0.11$), however, there was no significant group by time

interaction ($F_{2,72}=0.98$, $p=0.38$), and the change over time was not significantly different between the two groups ($F_{2,72}=0.02$, $p=0.90$). Bonferroni post hoc comparison revealed that the difference was significant between baseline and 4 weeks later (4.7 ± 0.3 vs. 5.5 ± 0.3 , $p=0.01$), and between one week later and 4 weeks (4.7 ± 0.3 vs. 5.5 ± 0.3 , $p=0.01$). For left pressure pain threshold, there was a significant difference over time ($F_{2,72}=8.4$, $p=0.001$, $\eta^2=0.20$), however, there was no significant group by time interaction ($F_{2,72}=0.48$, $p=0.59$), and the change over time was not significantly different between the two groups ($F_{2,72}=0.02$, $p=0.86$). Bonferroni post hoc comparison revealed that the difference was significant between baseline and 4 weeks later (4.5 ± 0.3 vs. 5.7 ± 0.4 , $p=0.005$), and between one week later and 4 weeks (4.5 ± 0.2 vs. 5.7 ± 0.4 , $p=0.001$). (Refer to **Table 3**).

Changes in NPRS

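### Left lateral flexion: the time effect's F and p are misprinted, and the interaction's F(2,72)=3.0 gives p=0.056, not the printed 0.03

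*Combined protocol and SAP*

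**What the plan says.** The Statistical Analyses section names the model: "Mixed factorial analysis of variance (ANOVA) was used to examine changes in cervical ROM variables" and the other outcomes. It specifies Bonferroni post hoc comparisons and a significance level of p≤0.05.

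Under Changes in ROM in the Results, the left lateral flexion paragraph reports:

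- Time effect: "There was a significant difference in mean ROM during left lateral flexion over time ($F_{2,72}=3.0$, $p=0.03$, $\eta^2=0.30".
- Interaction: "and a significant group by time interaction ($F_{2,72}=3.0$, $p=0.03".
- Post hoc, first pair: "baseline and one week later (43.0 ± 1.1 vs. 46.3 ± 1.0 , $p=0.01".
- Post hoc, second pair: "baseline and 4 weeks later (43.0 ± 1.1 vs. 48.5 ± 1.3 , $p<0.001".
- Post hoc, third pair: "between one week later and 4 weeks (46.3 ± 1.0 vs. 48.5 ± 1.3 , $p=0.01".

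The analysed sample is 38 (18 and 20), which fits the error degrees of freedom: 2 × (38 − 2) = 72.

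**The concern.** Two different effects in one model share the same F and the same p. That can happen by chance, but here the time effect also carries an η² and three post hoc results that point to a much larger F. At least one printed statistic must then be wrong.

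Two things are at stake. The first is the accuracy of the reported time effect. The second is the interaction, which tests whether the arms changed differently. Left lateral flexion is one of only three outcomes for which the Results report a significant interaction. If its F is right, its p is wrong, and the correct p lies on the other side of the 0.05 level.

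**Working it through.** **Inputs.** All come from the left lateral flexion paragraph: F=3.0 on 2,72 df; p=0.03; η²=0.30; means 43.0, 46.3 and 48.5; post hoc p-values 0.01, <0.001 and 0.01. N=38 gives 36 df for each pairwise comparison.

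**1. η² from F.** Partial η² = df1·F/(df1·F + df2) = 2×3.0/(2×3.0 + 72) = 6/78 = 0.077 (0.076–0.078 for F between 2.95 and 3.05). The printed value is 0.30. Inverting, F = 36·η²/(1 − η²):

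- η²=0.30 gives F=15.4.
- If 0.30 is a one-decimal rounding (0.25 to 0.35), F lies between 12.0 and 19.4.

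**2. Does the formula reproduce the document's other values?** GROC has 1,36 df; the rest have 2,72.

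| Outcome | F (time) | η² computed | η² printed |
|---|---|---|---|
| Extension | 6.8 | 0.159 | 0.20 |
| Right lateral flexion | 13.8 | 0.277 | 0.30 |
| Left lateral flexion | 3.0 | 0.077 | 0.30 |
| PPT right | 4.3 | 0.107 | 0.11 |
| PPT left | 8.4 | 0.189 | 0.20 |
| NPRS | 47.8 | 0.570 | 0.60 |
| GROC | 42.9 | 0.544 | 0.54 |
| NDI | 38.2 | 0.515 | 0.52 |

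Every row agrees to one or two decimals (NDI to within 0.005) except left lateral flexion, which is out by a factor of 3.9.

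**3. Time F from the post hoc results.** In this design F(time) = Σd²/ΣSE², summed over the three pairwise differences d and their standard errors. F is thus a weighted average of the three t² values and cannot fall below the smallest.

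- Differences are 3.3, 5.5 and 2.2, so Σd² = 10.89 + 30.25 + 4.84 = 45.98.
- Each SE is |d|/t, with t recovered from the printed p on 36 df and p<0.001 set to 0.001, which is conservative.
- Bonferroni-adjusted: t = 3.14, 3.97, 3.14; SE = 1.050, 1.387, 0.700; F = 45.98/3.52 = 13.1. The smallest t² is 9.9.
- Unadjusted: t = 2.72, 3.58, 2.72; SE = 1.213, 1.535, 0.809; F = 45.98/4.48 = 10.3. The smallest t² is 7.4.
- At the most lenient rounding of means and p-values, F is at least 12.5 (adjusted) or 9.6 (unadjusted).

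F=3.0 would need ΣSE² = 45.98/3.0 = 15.33, over three times what either reading gives. As a control, the unadjusted calculation gives 6.75 for extension (printed 6.8). For right lateral flexion the lower bounds are 10.2 (unadjusted) and 13.2 (adjusted), consistent with the printed 13.8.

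**4. p from F.** The upper tail of F(2,72) at 3.0 is 0.056 (0.054–0.059 for F between 2.95 and 3.05). The critical value at 0.05 is 3.12. A p of 0.03 needs F of about 3.68 (3.51–3.88 over rounding of p). This applies equally to the time row and the interaction row. The Change in NDI paragraph gives an internal comparison: there an interaction F of 2.8 on the same df is printed with p=0.07, and the formula gives 0.067.

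**The case against.** The strongest reply is that the time-effect error changes no stated conclusion. Time pools both arms, the misprint understates it, and the η² and post hoc results on the same line support the significance that the text claims. That stands. A reader might infer from F=3.0 and p=0.056 that range of motion did not change over time; the post hoc results contradict this.

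A reader might also infer that the interaction value is the misplaced one and that the between-arm result should be withdrawn. The documents do not support that. Since 3.0 cannot be the true time F, the interaction did not receive it from there, and 3.0 sits close to the other two ROM interaction values reported as significant (3.6 and 2.9). The separate percent-change comparison (20.0% vs. 7.7%, t=2.1) does not depend on either row; on 36 df its two-sided p is 0.043, still below 0.05 although not the printed 0.02.

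The η² mismatch alone is weaker evidence than it looks. A multivariate partial η² can exceed the univariate one: the baseline-to-4-week comparison, if Bonferroni-adjusted, implies at least 15.7/(15.7 + 36) = 0.304. Against this, the printed df are 2,72 and the other rows fit the univariate formula. The post hoc argument does not depend on η² at all. Nor should 0.30 be read as an effect of stretching; it is labelled as the effect over time.

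None of this reconciles the interaction's F with its p. A sphericity correction would only raise the p. Half of 0.056 is 0.028, which rounds to 0.03, but halving is not a valid one-sided version of a 2-df F test, and the NDI interaction p is not halved.

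**Conclusion.** The concern holds in two parts.

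- **Time effect.** The printed F and p are wrong. The line's own figures put F at about 13.1 (adjusted) or 10.3 (unadjusted), or 12.0–19.4 from η² alone. The exact value cannot be recovered because Table 2 is not shown, and copying from the interaction row remains only a plausible explanation. Significance over time very probably survives.
- **Interaction.** F(2,72)=3.0 and p=0.03 cannot both be right. Taking F as printed, p=0.056 and the result misses p≤0.05. Taking p as printed, F should be about 3.7. The text does not say which is the error, so it shows neither that the interaction is significant nor that it is not.

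The calculation assumes the printed df, 36 df for the post hoc tests, and error terms from the same model. The conclusions hold across rounding of F, the means and the p-values.

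**What to change.** Re-extract both left lateral flexion rows from the existing SPSS output. Replace the time F and p, confirm that the η² belongs to that test, and verify the interaction F and p against each other. If the interaction F of 3.0 on 2,72 df is confirmed, report p=0.056 and stop describing that interaction as significant. If instead p=0.03 is confirmed, correct the F.

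The right lateral flexion interaction should be checked in the same pass: its F(2,72)=2.9 gives p=0.061 against a printed 0.04. The cost is re-reading output that already exists and correcting a few figures; no new data or analysis is needed.

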Thirty-eight (38) subjects with a mean \pm SD age 30.9 ± 8.1 years and body mass index (BMI) 26.8 ± 6.7 kg/m² participated in the study. Sixty- five percent of the participants were females (n=

26). There was no significant difference between the two study groups in terms of age, Body Mass Index (BMI), cervical ROM and pressure pain threshold at baseline. Demographic and general characteristics are presented in **Table 1**.

Changes in ROM

Results of the mixed factorial ANOVA for ROM is displayed in **Table 2**. There was a significant difference in mean ROM during extension over time ($F_{2,72}=6.8$, $p=0.002$, $\eta^2=0.20$), and a significant group by time interaction ($F_{2,72}=3.6$, $p=0.02$). Bonferroni post hoc comparison revealed that the difference was significant between baseline and one week later (70.2 ± 2.1 vs. 74.3 ± 2.4 , $p=0.04$), baseline and 4 weeks later (70.2 ± 2.1 vs. 76.6 ± 2.0 , $p=0.001$), however, there was no significant difference between one week later and 4 weeks ($p=0.15$). In addition, the % improvement from baseline to 4 weeks later was significantly different between the combined intervention and standard intervention groups respectively (18.9% vs. 3.0% ; $t=2.4$, $p=0.02$). (Refer to **Table 2**)

Also, there was a significant difference in mean ROM during right lateral flexion over time ($F_{2,72}=13.8$, $p<0.001$, $\eta^2=0.30$), and a significant group by time interaction ($F_{2,72}=2.9$, $p=0.04$). Bonferroni post hoc comparison revealed that the difference was significant between baseline and one week later (40.8 ± 1.5 vs. 43.8 ± 1.3 , $p=0.03$), baseline and 4 weeks later (40.8 ± 1.5 vs. 46.8 ± 1.4 , $p<0.001$), and between one week later and 4 weeks (43.8 ± 1.3 vs. 46.8 ± 1.4 , $p=0.001$). In addition, the % improvement from baseline to 4 weeks later was significantly different between the combined intervention and groups respectively (23.2% vs. 10.8% ; $t=1.8$, $p=0.04$). (Refer to **Table 2**).

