There was a significant difference in mean NPRS over time ($F_{2,72}=47.8$, $p<0.001$, $\eta^2=0.60$), however, there was no significant group by time interaction ($F_{2,72}=1.5$, $p=0.23$), and the improvement did not differ significantly by study group ($F_{1,36}=1.4$, $p=0.24$). Bonferroni post hoc comparison revealed that the difference was significant between baseline and one week later (4.7 ± 0.3 vs. 3.3 ± 0.3 , $p<0.001$), baseline and 4 weeks later (4.7 ± 0.3 vs. 1.7 ± 0.3 , $p<0.001$), and between one week later and 4 weeks (3.3 ± 0.3 vs. 1.7 ± 0.3 , $p<0.001$).

Change in GROG

For GROG, there was a significant difference over time ($F_{1,36}=42.9$, $p<0.001$, $\eta^2=0.54$), however, there was no significant group by time interaction ($F_{1,36}=0.001$, $p=0.98$), and the improvement was not significantly different by study group ($F_{1,36}=0.7$, $p=0.40$). Bonferroni post hoc comparison revealed that the difference was significant between one week later and 4 weeks (2.4 ± 0.3 vs. 4.7 ± 0.4 , $p<0.001$). (Refer to **Table 3**).

Change in NDI

There was a significant difference in mean NDI over time ($F_{2,72}=38.2$, $p<0.001$, $\eta^2=0.52$), however, there was no significant group by time interaction ($F_{2,72}=2.8$, $p=0.07$), and the improvement over time did not differ by study group ($F_{1,36}=0.0$, $p=0.98$). Bonferroni post hoc comparison revealed that the difference was significant between baseline and one week later (11.2 ± 0.8 vs. 7.6 ± 0.7 , $p<0.001$), baseline and 4 weeks later (11.2 ± 0.8 vs. 4.5 ± 0.8 , $p<0.001$), and between one week later and 4 weeks (7.6 ± 0.7 vs. 4.5 ± 0.8 , $p<0.001$). After 4 weeks follow up, there were no significant changes in all the outcome variables by study group. (Refer to **Table 4**)

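### For flexion and both rotations, the claim that each group improved appears to rest on a time effect averaged over the two groups, which does not test that claim

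*Combined protocol and SAP*

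**What the plan says.** Under Changes in ROM, three directions (extension, right and left lateral flexion) are reported in detail. The other three, flexion and the two rotations, share one sentence: "both groups had a significant improvement in mean ROM over time ($p<0.05$), however, this improvement was not significantly different between the two groups". It refers to Table 2 and gives no F statistic, degrees of freedom, means or per-arm figures.

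Statistical Analyses names these methods for change:
- "Mixed factorial analysis of variance (ANOVA) was used to examine changes in cervical ROM variables" and the other outcomes, by group over time.
- "Post hoc comparisons using Bonferroni test and effect size were computed to identify significant differences over time".
- A between-arm comparison of percent change from baseline to 4 weeks, by t-test and Mann-Whitney test.
- "To examine whether there were any changes in the outcome variables at 4 weeks follow up paired t- test was used".

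The significance level is 0.05. Procedures gives the arm sizes as 18 (combined) and 20 (standard).

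**The concern.** That both groups improved is two statements per direction, one for each arm. The time main effect of a two-group mixed ANOVA has a single null hypothesis: the change averaged over the arms is zero. Rejecting it says that the average moved. It does not say that each arm moved.

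The trial asks what stretching adds to standard care. Gains in both arms, and a gain in one arm with a difference that a small trial missed, are different findings. The sentence presents the first for three of the six ROM directions, and the test that seems to lie behind it cannot separate the two.

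**Working it through.** **1. Which described test could support the sentence?**
- *Mixed ANOVA time effect and Bonferroni comparisons.* Every post hoc comparison printed in the Results gives one mean per visit, pooled over arms (for extension, 70.2 at baseline and 76.6 at 4 weeks). No within-arm comparison is named.
- *Percent-change tests.* These compare the arms with each other.
- *Paired t-test.* It is tied to the 4-week follow-up. Data collection describes week 8 as the follow-up for maintained gains, one month after the interventions. The result reported at the end of Change in NDI is "After 4 weeks follow up, there were no significant changes in all the outcome variables by study group". A test with that result is not a likely source of a significant improvement.

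The arm-averaged time effect is what remains.

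**2. Can the stated p<0.05 be reproduced?** Not for these three directions, because no inputs are printed. As a check on the model, the time effects printed elsewhere do reproduce: F(2,72)=6.8 for extension gives p=0.0020 (stated 0.002), and F(2,72)=4.3 for right pressure pain threshold gives p=0.017 (stated 0.02).

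**3. What can the time effect hide?** Let d1 and d2 be the observed week-4 gains in the combined and standard arms. Assume the same shape over visits in both arms and equal weighting of the arms. Then F_time is proportional to (d1+d2)² and F_interaction to (d1−d2)², with the same constant, so

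F_interaction = F_time × [(d1−d2)/(d1+d2)]².

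Illustration, assuming linear change and error variance 1:
- Take F_time=3.8 (p=0.027) and d2=0.1×d1.
- F_interaction = 3.8 × (0.9/1.1)² = 2.54, p=0.086.
- The effective n is 4/(1/18+1/20)=37.9 and F_time = 37.9×g²/4, where g is the average gain. So g=√(4×3.8/37.9)=0.633, d1=2×0.633/1.1=1.15 and d2=0.115.
- Paired tests, with SD of change √2: combined arm t=1.15/√(2/18)=3.45, p=0.003; standard arm t=0.115/√(2/20)=0.36, p=0.72.

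Time is significant and the interaction is not, as reported, yet only one arm shows a demonstrable gain.

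**4. How often would this arise?** The simulation used 18 and 20 participants, three visits, F tests on 2 and 72 df, and 20,000 trials per setting. Assumptions not in the documents: compound symmetry, the SD of the change score set to 1, one arm with zero true change, and a one-week gain of 60% of the other arm's week-4 gain d.

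| d (SD of change) | Time significant | Time significant, interaction not |
|---|---|---|
| 0.25 | – | 8% |
| 0.5 | 25% | 18% |
| 0.75 | 52% | 24% |
| 1.0 | 78% | 16% |
| 1.25 | – | 6% |
| 1.5 | – | 1% |

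If the standard arm is the one that improves, the last column at 0.5, 0.75 and 1.0 is 19%, 25% and 17%. With no change in either arm, the time test rejects in 5%. Under a different set-up (between-visit correlation 0.5 to 0.8, combined-arm gain 0.4 to 1.0 SD of the outcome, one-week gain half of the week-4 gain), the pattern arises in 0.7% to 24% of trials.

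**The case against.** The strongest reply is that Table 2 is not in the available text. It is introduced as mixed ANOVA output, but it is also cited straight after the per-arm percent gains for extension, so per-arm results for flexion and rotation may be there. The wording about the paired t-test names neither the comparator visit nor the arm, and the follow-up result is reported by study group, so within-arm tests may have been run. This stands, and it makes the point conditional. It does not remove it, because no method for a within-arm test from baseline to week 4 is clearly stated.

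Three stronger readings are tempting, and the documents do not support them.
- *One arm did not improve at all.* No data for these directions are printed. If the reported lack of difference is the interaction test, an observed change of exactly zero in one arm is in fact excluded: with d2=0 the formula above gives F_interaction=F_time, so both would be significant. A true change of zero, or an observed gain of about a tenth of the other arm's, is not excluded.
- *Extension proves the error.* Its time effect is p=0.002 with gains of 18.9% and 3.0%, which shows that a strong average can sit beside a small gain in one arm. But an interaction was declared there, and no claim about both groups was made.
- *The misleading pattern runs at several times the 5% level.* That holds only near the peak. The rate is 6% at 1.25 SD and 1% at 1.5 SD.

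It is also fair to say that the text reports no significant difference rather than similar gains, and that the add-on question is answered by the between-arm contrast, which was tested.

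**Conclusion.** The point holds, subject to Table 2. For flexion and both rotations, a per-arm conclusion is drawn where the methods clearly describe only an arm-averaged test, and non-significance between arms of 18 and 20 does not turn it into evidence for each arm. The simulated rates of about 1% to 25% depend on the assumed zero change in one arm and on the size of the other arm's change. They show that the reported pattern is compatible with improvement in only one arm. They do not estimate how likely that is in this trial.

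**What to change.** - Under Changes in ROM, replace the sentence with wording such as: *averaged over the two groups, mean ROM increased over time; a difference between the groups was not detected*.
- For these three directions, report each arm's mean change from baseline to week 4 with a 95% CI, and the between-arm difference in change with a 95% CI. Present them as description.
- Do not add a rule that both arms' intervals must exclude zero. Even with equal true gains of 0.3 to 0.6 SD (correlation 0.5 to 0.7), both arms pass a paired test in only 17% to 81% of simulated trials showing this pattern, and such a rule invites readings based on one arm being significant and the other not.
- If within-arm tests were run, name them in Statistical Analyses with the visits compared.

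The cost is one sentence, six within-arm estimates and three between-arm estimates from data already collected. The downside is a slightly weaker stated conclusion.
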